5.2 SECONDARY ENDPOINTS

5.2.1 Key secondary endpoints

Not applicable.

5.2.2 Other secondary endpoints

5.2.2.1 First part

There are no secondary endpoints.

Proprietary confidential information © 2017 Boehringer Ingelheim International GmbH or one or more of its affiliated companies

5.2.2.2 Second part

Time to OR

Time to objective response is defined as the time from first treatment administration until first documented CR or PR.

Time to objective response will only be calculated for patients with an objective response:

- Time to OR [days] = date of first documented CR or PR - date of first treatment administration + 1.

Duration of OR

Duration of objective response is defined as the time from first documented CR or PR until the earliest of disease progression or death among patients with objective response.

Duration of objective response will only be calculated for patients with an objective response. For patients with disease progression or death:

- Duration of objective response [days] = date of outcome – date of first assessment indicating OR + 1.

For patients without disease progression or death:

- Duration of objective response (censored) [days] = date of outcome – date of first assessment indicating objective response + 1

The censoring rules for duration of OR are given in Table 5.2.2.2: 1.

Table 5.2.2.2: 1 Derivation rules for Duration of Objective Response

Situation	Outcome (event or censored)	Date of outcome
No other anti-cancer therapy		
Alive and not progressed, no more than one consecutively missed radiological assessments	Censored	Date of last radiological assessment
Alive and not progressed, two or more consecutively missed radiological assessments	Censored	Date of last radiological assessment prior to missed radiological assessments
Progressed, zero or one missed radiological assessment prior to progression	Event	Date of radiological assessment of progression
Progressed, but two or more consecutively missed radiological assessments prior to progression	Censored	Date of last radiological assessment prior to missed assessments

Proprietary confidential information © 2017 Boehringer Ingelheim International GmbH or one or more of its affiliated companies

Table 5.2.2.2: 1 Derivation rules for Duration of Objective Response (cont.)

Situation	Outcome (event or censored)	Date of outcome
Death but no progression, zero or one missed radiological assessment prior to death	Event	Date of death
Death without progression, but two or more consecutively missed radiological assessments prior to death	Censored	Date of last radiological assessment prior to missed assessments
Initiation of subsequent anti-cancer therapy		
Subsequent anti-cancer therapy started before progression or death, no more than one consecutively missed radiological assessments prior to start of subsequent anti-cancer therapy	Censored	Date of last radiological assessment before initiation of subsequent anti-cancer therapy

Only radiological assessments after first assessment indicating objective response will be taken into consideration.

Disease control (DC)

DC is defined as best overall response of CR or PR or SD where best overall response is defined according to RECIST version 1.1 (see Appendix 10.5 of the CTP) from first administration of trial medication until the earliest of disease progression, death or last evaluable tumour assessment before start of subsequent anti-cancer therapy.

Note that an adequate tumour assessment includes an assessment of target lesions, as well as radiological tests to evaluate non-target lesions and to search for new lesions, i.e. a RECIST tumour evaluation. If no RECIST tumour evaluation has been performed, the assessment will be set to missing.

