###### Secondary endpoints

- Disease control (DC), defined as complete response (CR), partial response (PR) or stable disease (SD).
- Time to objective response, defined as the duration of time from the date of first treatment administration until objective response.
- Duration of objective response, defined as the duration of time from first objective response to the date of first objective tumour progression or death due to any cause.

Patients with measurable and evaluable disease should have assessment according to [RECIST version 1.1](#).

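### The duration-of-response table discards documented response time after a closed scan gap and leaves some progressions, deaths and therapy starts without a row

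*SAP*

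**What the plan says.** Protocol 5.1.1.2 defines duration of response as the "duration of time from first objective response to the date of first objective tumour progression or death due to any cause", with no condition on missed scans. SAP 5.2.2.2 repeats that definition and then adds derivation rules in Table 5.2.2.2: 1. With no new anti-cancer therapy, the rows come in three pairs:

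- **Alive.** "Alive and not progressed, no more than one consecutively missed radiological assessments" is censored at the last scan. "Alive and not progressed, two or more consecutively missed radiological assessments" is censored at the last scan before the missed ones.
- **Progressed.** "Progressed, zero or one missed radiological assessment prior to progression" is an event. "Progressed, but two or more consecutively missed radiological assessments prior to progression" is censored, dated "Date of last radiological assessment prior to missed assessments".
- **Died.** "Death but no progression, zero or one missed radiological assessment prior to death" is an event. "Death without progression, but two or more consecutively missed radiological assessments prior to death" is censored at the same kind of date.

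A single further row covers new anti-cancer therapy. It applies when no more than one consecutive scan was missed before that therapy began, and it censors at the last scan before the therapy. A note limits all rows to scans after the first response. SAP 6.7.2 assigns each image to a nominal window and counts a window with no image as missed. SAP 7.5.2.2 shows duration patient by patient, with a cohort summary only if applicable.

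**The concern.** A missed-scan rule exists so that a progression is not dated across a stretch in which nobody looked. It has work to do only when the unobserved stretch comes directly before the event. If the patient was scanned again after the gap and had not progressed, the gap has been closed and carries no doubt about the later event date.

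The table does not make that distinction. The alive row with a gap has no limit on where the gap lies. The progression and death rows with a gap do not require it to be immediately before the event. The pairs are also not complementary: the event rows count missed scans in total, while the censoring rows count consecutive ones. A patient can fall between them, and the outcome would then have to be settled after the open-label data are known. With few responders, each listed individually, one misclassified long responder would be plainly visible in the results.

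**Working it through.** **1. Scan grid.** SAP 6.7.2 gives due day = week × 7 + 1. Weeks 8, 16, 24, 32, 40, 48 and 56 give days 57, 113, 169, 225, 281, 337 and 393. Rebuilding the windows from the footnote reproduces every printed bound. Missing weeks 24 and 32 means no image from day 142 to day 253, that is 253 − 142 + 1 = 112 days.

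**2. Alive rows.** If no scan follows the gap, the last scan is also the last scan before the gap, and both rows give the same date. They differ only when scanning resumed. So the gap row can only remove observed follow-up.

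**3. Worked patient.** First response at day 57, scan at day 113, weeks 24 and 32 missed, still responding at days 281 and 337. Duration = outcome date − day 57 + 1; months = days × 12 ÷ 365.25 (SAP 7).

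| Last status | Table as worded | Gap counted only if immediately before the event; living patients censored at last scan |
|---|---|---|
| Alive, last scan day 337 | 113 − 57 + 1 = 57 days, censored (1.9 months) | 337 − 57 + 1 = 281 days, censored (9.2 months) |
| Progression at day 393 | 57 days, censored (1.9 months), read literally | 393 − 57 + 1 = 337 days, event (11.1 months) |

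The progression lies between the scans at days 337 and 393, both attended, so its date is well bracketed.

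**4. Which patterns fit which row.** Take response at week 8 and progression at week 56. Five scans lie between (weeks 16 to 48), giving 2⁵ = 32 attended/missed patterns:

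- 6 are events (zero or one miss);
- 8 are censored with the gap immediately before progression, which is the rule's proper use;
- 11 are censored only because of an earlier gap, on the literal reading;
- 7 fit neither row (two or more misses, none consecutive).

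Death in place of progression divides the same way. The alive pair and the therapy row are worded by consecutive misses, so they do cover non-consecutive ones. The therapy row has no partner for two or more consecutive misses.

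**5. How often.** The documents give no miss rate. Assuming independent misses of 5%, 10% or 20% per scan:

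| Scenario | Earlier gap only | No row |
|---|---|---|
| Progression at week 56 | 0.7% / 2.7% / 9.5% | 1.3% / 4.5% / 12.8% |
| Same, week 16 scan always attended (four free scans) | 0.5% / 1.8% / 6.4% | 0.7% / 2.4% / 7.7% |
| Progression at week 40 | 0.2% / 0.9% / 3.2% | 0.2% / 0.9% / 3.2% |
| Progression at week 32 or earlier | 0 | 0 |

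**6. Number of patients.** Protocol 7.6 plans 18 Part B patients. Its 73% chance of at least 3 responses at a 20% rate is reproduced (0.72866). Expected responders are 18 × 0.15, 0.20 and 0.25 = 2.7, 3.6 and 4.5. If all 3.6 progressed at week 56, the expected number affected by either problem would be 3.6 × 2.0% = 0.07, 3.6 × 7.2% = 0.26 and 3.6 × 22.3% = 0.80 at the three miss rates.

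**The case against.** The best defence starts with the words. The progression and death rows never say that a gap anywhere in follow-up counts; *prior to* can be read as *immediately prior to*, and only scans after first response are considered. Zero or one missed can likewise be read as the intended complement of two or more consecutively missed. Both readings are possible, but the text does not settle them, and the neighbouring alive row is plainly not limited by position. A programmer could code the literal version in good faith. Censoring a progression found directly after a long gap is a deliberate choice and is not disputed.

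A reader might infer that the literal rule biases duration of response downwards. The documents do not support that for Kaplan-Meier summaries. SAP 7 reports time-to-event data as events, censored patients and percentiles, and a patient cut short here is marked censored. Simulation on the SAP grid with independent misses gave these proportions still responding at about 11 months:

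| Assumed median, miss rate | Complete scans | Literal table | Immediately-prior rule |
|---|---|---|---|
| 6 months, 10% | 0.278 | 0.283 | 0.288 |
| 6 months, 20% | 0.279 | 0.288 | 0.308 |
| 12 months, 20% | 0.527 | 0.531 | 0.551 |

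The literal table does not shorten the estimate. The narrower rule moves it up slightly more, because it censors patients who progress directly after a gap and keeps those still responding.

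It is also fair that a two-scan gap is a long absence from imaging, that Protocol 5.1.2 keeps the scan schedule fixed through treatment interruptions, and that the endpoint is secondary in a trial with no formal tests (Protocol 7.2). These points limit how often the problem arises. They do not touch the alive row, whose effect is independent of how *prior to* is read.

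**Conclusion.** The point holds as a drafting defect with limited reach. Three things follow from the text alone: the alive row with a gap only ever removes documented response time; the position of the gap is unspecified in the progression and death rows; and two situations have no row, namely progression or death after two or more non-consecutive misses, and new therapy after two or more consecutive misses.

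Two stronger readings should be resisted. Non-consecutive misses are not unhandled across the whole table, only in the progression and death pairs. And a patient with no row is unclassified rather than a discarded progression; loss of an observed event follows only from the literal reading of the consecutive-miss rows.

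For an affected patient the effect is large: 57 days against 281 or 337 in the example. Across the trial it probably concerns zero or one patient among roughly 3 to 5 expected Part B responders, plus any Part A responders in the RP2D pool. The frequencies rest on assumed, independent miss rates and an assumed time of progression. Objective response, the primary endpoint, is unaffected.

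**What to change.** In SAP Table 5.2.2.2: 1:

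1. In the progression and death censoring rows, require the two or more consecutive misses to be *immediately prior to* progression or death, and date the censoring at the last scan before that gap.
2. In the matching event rows, require *no more than one consecutively missed assessment immediately prior to* progression or death, so that each pair covers every pattern.
3. Censor living, non-progressed patients at the last adequate radiological assessment, whatever gaps came earlier.
4. Add the missing row for two or more consecutive misses before new anti-cancer therapy. The last adequate assessment before that therapy would match item 3.

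The cost is SAP wording and the matching derivation code. The statistical price is the slightly selective censoring shown in the simulation, which can move a Kaplan-Meier estimate up a little. A progression that arose inside a gap and was no longer evident at the next scan would also go undetected, which is unlikely under RECIST.

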5.4.2 Treatment exposure

Total treatment duration [days]:

Date of last administration of any trial medication – date of first administration of any trial medication + 1.

Total treatment duration therefore includes time when treatment was temporarily discontinued and subsequently reintroduced.

Duration of specific medication exposure [days]:

Date of last administration of specific medication – date of first administration of specific medication + 1.

Duration of specific medication exposure will be calculated separately for xentuzumab and afatinib.

Number of courses initiated [N]:

Course initiated means that the patient received at least one administration of trial medication in the initiated course.

Total number of xentuzumab infusions [N]:

Sum of xentuzumab infusions calculated across all courses.

It will be calculated for each patient who received at least one infusion of xentuzumab.

Number of patients with at least one dose reduction [N]

Number of patients with at least one dose reduction will be counted.

Proprietary confidential information © 2017 Boehringer Ingelheim International GmbH or one or more of its affiliated companies

The number of patients with at least one dose reduction will first be calculated for any medication and then separately for each specific medication for which dose reduction is allowed. This means that it will be calculated separately for xentuzumab and afatinib.

Time to first dose reduction of specific medication [days]:

Date of first administration of the first reduced dose of specific medication – date of first administration of specific medication + 1.

Time to first dose reduction will be calculated only for patients who had a dose reduction.

This will also be calculated separately for patients with a dose reduction of xentuzumab or afatinib.

Total dose of specific trial medication [mg]:

Total dose of trial medication will be calculated separately for xentuzumab and afatinib.

For xentuzumab, this is the sum of the administered doses calculated across all courses. This takes into account the dose reductions.

For afatinib, this is calculated as the total duration of treatment with this medication in days multiplied by the actual dose taken (using the actual dose recorded on the Case Report Form (CRF)) for the days the medication was taken. This takes into account the dose reductions of afatinib. This calculation is only an approximation of the total dose taken, since the way the data are collected do not allow a more precise calculation.

Dose intensity of specific trial medication during all treatment duration (%):

Dose intensity of trial medication will be calculated separately for xentuzumab and afatinib.

$100 * (\text{Total dose of specific trial medication actually received by a patient} / \text{Planned total dose of specific trial medication during the entire duration of treatment})$.

The planned total dose is calculated as the total dose of the medication a patient should have received from the date of first administration of the medication to the date of last administration.

The planned total dose of xentuzumab for each patient is calculated using the following formula: planned dose per infusion (e.g. 1000 mg) multiplied by number of visits with administration of xentuzumab.

For afatinib, the planned total dose for each patient is calculated using the following formula: total duration of treatment with this medication in days multiplied by the planned daily dose (e.g. 40 mg, using the dose the patient was initially assigned to).

This is done assuming that the initial dose was taken throughout, and dose reduction as specified in the protocol will not be considered in the calculation. This means that if a patient had protocol-defined dose reduction due to an Adverse Event (AE), the reduced dose will not be used in the calculation of the denominator.

For afatinib, this calculation is only an approximation of the dose intensity, since the way the data are collected does not allow a more precise calculation.

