Name of finished product: N.A.				
Name of active ingredient: Xentuzumab (BI 836845)				
Protocol date: 28 Mar 2014	Trial number: 1280.16		Revision date: 02 Nov 2016	
Duration of treatment: Continuous treatment until disease progression, intolerable adverse events (AEs), consent withdrawal or non-compliance with the study protocol				
Criteria for efficacy: Primary endpoint (for Part B) 

• Objective response (OR), defined as complete response (CR) or partial response (PR) according to RECIST v1.1

 Secondary endpoints (for Part B) 

• Disease control, defined as complete response (CR), partial response (PR) or stable disease (SD)

• Time to objective response, defined as the duration of time from the date of first treatment administration until objective response

• Duration of objective response, defined as the duration of time from objective response to the date of first objective tumour progression or death due to any cause

				
Criteria for safety: 

• MTD of Xentuzumab (BI 836845) in combination with afatinib (primary endpoint for Part A only)

• Dose limiting toxicity (DLT) during the first treatment course (primary endpoint for Part A only)

• Adverse Events (AEs) according to Common Terminology Criteria (CTCAE version 4.03), physical examination, vital signs, ECOG performance score, safety laboratory parameters, electrocardiogram (ECG), and Left Ventricular Ejection Fraction (LEVF)

				
Statistical methods: Descriptive and exploratory analyses				

Proprietary confidential information.

© 2016 Boehringer Ingelheim International GmbH or one or more of its affiliated companies. All rights reserved.

This document may not - in full or in part - be passed on, reproduced, published or otherwise used without prior written permission.

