6.6 HANDLING OF MISSING DATA AND OUTLIERS

In general, missing data will not be imputed, unless required for the following analyses and definitions. Then the rules as described below apply.

Missing dates that affect the evaluation of endpoints specified in previous sections of this TSAP will be imputed utilising a “worst case” approach, which will be applied on a case-by-case basis (depending on the affected endpoint) and agreed to by the trial team members at the final BRPM before database lock at the latest.

The rules in the table 6.6: 1 below have been agreed by the trial and project teams, and will be used in this trial, if applicable.

Table 5.3.2.2:1 Rules for imputations of missing or incomplete dates

Date	Imputation rule
Date of birth	In case only the year is given: 1 st of January
Date of death	Date last known to be alive. If only year and month are given: this will be imputed with 1 st of the month for the analysis of OS
Date of first histological diagnosis	1 st of month if day is missing 1 st of January if month also missing
Date of start of concomitant medication	No imputation required
Date of end of concomitant medication	No imputation required
Date of start of subsequent anti-cancer therapy (imputation required only for censoring of PFS)	If the day (respectively day and month) of the start date of subsequent anti-cancer therapy is missing, then the first of the month (respectively 1st January) will be imputed unless this date leads to a date before the stop date of study medications. In this case, the study medications stop date + 1 day will be imputed. Additionally, all imputed start dates of subsequent anti-cancer therapy should be before death date if available.
Date of stop of subsequent anti-cancer therapy	No imputation required
Date of end of treatment (only for patients still ongoing at time of snapshot/DBL)	Date of snapshot If date of death before this date, use date of death

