7 PLANNED ANALYSES

The labelling and display format of statistical parameters will follow BI standards (7).

Unless otherwise specified, outputs will be displayed separately for each part of the trial.

With protocol amendment 4, starting doses of xentuzamab 1000mg + afatinib 30mg and xentuzamab 1000mg + afatinib 20mg are also allowed in part B. For part B, sections for trial subjects and safety analyses will be displayed by starting dose and total. Efficacy analyses will be done for part B patients, and RP2D patients (defined as pooled patients of all the patients in part B and the patients starting with xentuzumab 1000mg + afatinib 40mg in part A excluding squamous carcinoma patients).

Descriptive statistics for continuous variables will generally contain N (number of patients in that patient set with non-missing values), Mean, Standard Deviation, Minimum (Min), Q1 (25th percentile), Median, Q3 (75th percentile), Maximum (Max). In general, means, standard deviations, medians, Q1 and Q3 will be presented to one more decimal place than the raw data. Minima and maxima will be presented to the same number of decimal places as the raw data.

For time-to-event analysis tables, the set of statistics is: number of patients [N (%)], Number of patients with event [N (%)], Number of patients censored [N (%)], <Time to event> [months] followed by P25 (25th percentile), Median, P75 (75th percentile). If not specified otherwise, the duration as well as time to event will be displayed in months.

Tabulations of frequencies for categorical data will include all possible categories and will display the number of observations in a category as well as the percentage (%) relative to the respective treatment group total. Percentages will be rounded to one decimal place.

In general a category “missing” will be displayed, if there are missing data for the corresponding variable. Percentages will also generally be based on all patients in the respective patient set whether they have non-missing values or not.

Sort order for general categorical variables: If categories correspond to the collected categories on the eCRF and the table shells do not explicitly specify the ordering, the “default ordering” defined by the eCRF is to be used in such cases. If categories are derived the ordering as specified in the table shell document should be used; in general ordinal data (e.g. categorised continuous data) are to be displayed in ascending order.

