7.7 EXTENT OF EXPOSURE

The variables defined in [Section 5.4.2](#) will be summarised descriptively for each dose cohort.

Proprietary confidential information © 2017 Boehringer Ingelheim International GmbH or one or more of its affiliated companies

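### Time to first dose reduction is summarised only in patients who had a reduction, so the median comes out early and moves with time on treatment (minor, descriptive)

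*SAP*

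**What the plan says.** SAP 5.4.2 defines time to first dose reduction, separately for xentuzumab and afatinib, as "Date of first administration of the first reduced dose of specific medication – date of first administration of specific medication + 1". It then limits who contributes: "Time to first dose reduction will be calculated only for patients who had a dose reduction". No censoring or competing-event rule is given for the others. The same section provides a companion count: "Number of patients with at least one dose reduction will be counted". It also defines duration of exposure and dose intensity for each drug.

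SAP 7.7 says the 5.4.2 variables "will be summarised descriptively for each dose cohort". For Part B, SAP 7 adds: "For part B, sections for trial subjects and safety analyses will be displayed by starting dose and total". That this display covers the exposure tables is a reasonable inference, but it is not stated.

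The protocol synopsis gives the duration of treatment as "Continuous treatment until disease progression, intolerable adverse events (AEs), consent withdrawal or non-compliance with the study protocol". Time at risk of a reduction therefore differs between patients. The SAP 6.6 date-imputation table also provides for patients still on treatment at a snapshot or database lock.

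**The concern.** The summary conditions on the event having been observed. A patient who stops for progression without a reduction contributes nothing, although that patient's time at the starting dose is information. Among those who do contribute, only times shorter than their own time on treatment can appear.

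Two misreadings follow. One is to quote the median as the typical time to a first reduction. The other is to compare it between dose cohorts or Part B starting doses and take a difference as one of tolerability, when different treatment durations alone can produce it.

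**Working it through.** The documents state no figure for time to dose reduction, so there is none to reproduce. The check is on direction and dependence.

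**Direction, without a model.** Count the patients without a reduction as not yet reduced and put them back. The time by which half of the group has been reduced can then only stay the same or move later. The reducers-only median is therefore the early one.

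**Dependence on time on treatment.** Let T be time to first reduction and C time on that drug. The planned statistic is the median of T given T ≤ C. For independent exponential times with medians mT and mC:

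- reducers-only median = 1 / (1/mT + 1/mC)
- share of treated patients reduced = mC / (mT + mC)

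Inputs, all assumed: mT = 4 months, and mC = 2, 4.5 and 9 months. The middle value borrows the 4.5-month PFS that Protocol 2.1 quotes for afatinib in patients with acquired resistance, used here as if it were median time on treatment.

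| mC (months) | Reducers-only median (months) | Share reduced | Half of all treated patients reduced by (months) |
|---|---|---|---|
| 2 | 1/(1/4 + 1/2) = 1.33 | 2/6 = 33% | never |
| 4.5 | 1/(1/4 + 1/4.5) = 2.12 | 4.5/8.5 = 53% | 8.8 |
| 9 | 1/(1/4 + 1/9) = 2.77 | 9/13 = 69% | 5.1 |

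The underlying rate of reduction is the same in all three rows, yet the planned median doubles from the first to the last. It also points the wrong way as a guide to burden: the group with the latest median has the most patients reduced. Simulation with 1,000,000 patients per scenario agreed with the formula to within 0.01 month.

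**Sensitivity to the shape of the hazard** (mC = 2 / 4.5 / 9 months):

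- Declining Weibull hazard (shape 0.6), underlying median 4 months: 0.60 / 1.08 / 1.63 months.
- Only 40% of patients ever need a reduction, with a median of 1 month among them: 0.67 / 0.82 / 0.90 months, which is 0.33 / 0.18 / 0.10 month short of 1.

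The shift is thus small when reductions are confined to the first weeks in a susceptible subset. A rate that merely declines but continues does not make it small.

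**The case against.** The restriction is stated openly, and the SAP does not present the result as an all-patient estimate. The number of patients reduced, exposure duration and dose intensity are planned as well, and SAP 7.8.1 tabulates adverse events leading to reduction and to discontinuation. No test or model uses the variable (Protocol 7.2, SAP 6.5). Since the Part B primary analysis follows the last patient's first follow-up visit, treatment should be essentially complete. The share reduced multiplied by the reducers-only distribution then gives the observed cumulative incidence. All of this stands and keeps the point minor. What the planned summaries still do not show is how many patients had been reduced, and how many had stopped the drug unreduced, by a fixed time.

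Three stronger readings are tempting and are not supported.

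- A reader might infer that the variable bears on the choice of RP2D. Protocol 4.1.3.2 records that the RP2D has already been determined. The exposure items that SAP 9.1 lists for that decision are treatment duration and patients with a reduction, not time to reduction.
- A reader might infer a large distortion. Medians of 6 months to reduction and 3 months to stopping would give 1/(1/6 + 1/3) = 2.0 months, but both inputs and the constant rates are assumptions. Protocol 4.2.3.1 says diarrhoea usually starts within two weeks, and Table 4.1.4.3: 1 makes persistent Grade 2 diarrhoea a trigger for afatinib reduction, so early reductions are plausible.
- A reader might infer that Kaplan-Meier with censoring at last dose is the remedy. It would treat stops for toxicity as unrelated to the need for a reduction. It would mislead most for Part B patients starting afatinib at 20 mg, who under Protocol 4.1.4.3 normally discontinue it rather than reduce. That group could look almost free of reductions despite toxicity stops.

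**Conclusion.** The point holds as a minor improvement. The reducers-only median is earlier than an all-patient estimate and varies with time on treatment, so differences between dose groups can come from treatment duration alone. The direction rests on the definition in SAP 5.4.2. The sizes rest on assumed reduction and stopping rates, because the documents give none for this trial. In the scenarios above, the shortfall runs from 0.10 month with early, confined reductions to more than 2 months in some cases. The measure describes tolerability. It does not affect the primary endpoints, any test or the RP2D decision.

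**What to change.** In SAP 5.4.2 and 7.7, for each drug and in all patients who received it, report by dose group the cumulative incidence of first dose reduction at the end of courses 1, 2 and 3 (28, 56 and 84 days). Treat permanent discontinuation of that drug without a prior reduction as a competing event and show its cumulative incidence alongside. Censor patients still on the drug at the data cut-off. If nobody is censored before 84 days, each figure is simply a count over the number treated.

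Cumulative incidence also depends on how long patients stay on treatment, as the last column of the table shows. That is why the discontinuation figures must stand beside it.

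Keep the reducers-only times as a listing, or as a summary labelled 'among patients with a reduction' with n/N and exposure duration next to it.

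The cost is a change of SAP wording and one extra table. The dates of first dose, first reduced dose and last dose of each drug are already used in 5.4.2, and reasons for discontinuation are already tabulated under SAP 7.1.1. With 18 patients planned in Part B, split by starting dose, the estimates in the smaller groups will be imprecise.
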